## 6 Primary and Secondary Outcome Variables

### 6.1 Primary Safety Variables

Safety and tolerability are based on reported adverse events (AEs), vital signs, ECG parameters, clinical laboratory test results (including blood/serum chemistry, hematology, urinalysis), physical examinations, EPS rating scales (including Simpson-Angus Neurologic Rating Scale [SAS], Abnormal Involuntary Movement Scale [AIMS], and Barnes Akathisia Rating Scale [BARS]), Visual Analog Scale (VAS) scores for pain perception, investigator's assessment of most recent injection site, and suicidality via C-SSRS.

Protocol 031-201-00181

## 6.2 Primary Pharmacokinetics Variables

The primary PK parameters to be estimated for aripiprazole are as follows:

- Plasma concentration of aripiprazole 56 days postdose ( $C_{56}$ ) of aripiprazole 2M LAI 960 mg after the fourth dose and plasma concentration of aripiprazole 28 days postdose ( $C_{28}$ ) of aripiprazole IM depot 400 mg after the eighth dose over the course of 32 weeks;
- $AUC_{0-56}$  for aripiprazole 2M LAI 960 mg after the fourth dose, and sum of  $AUC_{0-28}$  for aripiprazole IM depot 400 mg after the seventh dose and eighth doses over the course of 32 weeks, based on the PK data from subjects enrolled to the robust sampling schedule.

## 6.3 Secondary Pharmacokinetics Variables

The following secondary PK parameters are estimated for aripiprazole after the administration of aripiprazole 2M LAI 960 mg and aripiprazole IM depot 400 mg:

- $C_{max}$  and  $t_{max}$  after the first and fourth doses of aripiprazole 2M LAI 960 mg;
- $AUC_{0-56}$  and  $C_{56}$  after the first dose of aripiprazole 2M LAI 960 mg;
- $AUC_{0-28}$  and  $AUC_{29-56}$  after the fourth dose of aripiprazole 2M LAI 960 mg;
- Peak-to-trough percent fluctuation (PTF%) after the fourth dose of aripiprazole 2M LAI 960 mg;
- $C_{max}$  and  $t_{max}$  after the first, seventh and eighth doses of aripiprazole IM depot 400 mg;
- $AUC_{0-28}$  and  $C_{28}$  after the first dose of aripiprazole IM depot 400 mg;
- PTF% after the eighth dose of aripiprazole IM depot 400 mg.

$C_{max}$ ,  $t_{max}$ , AUC, and PTF% are determined only from subjects enrolled to the robust sampling schedule;  $C_{56}$  and  $C_{28}$  are determined from subjects enrolled to the sparse and robust sampling schedule.

The following PK parameters are estimated for aripiprazole after administration of aripiprazole 2M LAI 960 mg + oral aripiprazole 10 to 20 mg for 7 days and aripiprazole IM depot 400 mg + oral aripiprazole 10 to 20 mg for 14 days (this endpoint is only for subjects enrolled to the robust sampling schedule):

- Plasma concentration of aripiprazole 7 days postdose ( $C_7$ )
- Plasma concentration of aripiprazole 14 days postdose ( $C_{14}$ ).

## 6.4 Secondary Efficacy Variables

The efficacy of aripiprazole IM depot administration in the gluteal muscle is assessed by the Positive and Negative Syndrome Scale (PANSS; schizophrenia subjects only), Clinical Global Impression Severity (CGI-S; schizophrenia subjects only), Clinical

Protocol 031-201-00181

Global Impression - Improvement (CGI-I), Subjective Well-being under Neuroleptic Treatment-Short Form (SWN-S), Montgomery-Asberg Depression Rating Scale (MADRS; bipolar subjects only), Young Mania Rating Scale (YMRS; bipolar subjects only), and Clinical Global Impression - Bipolar Version (CGI-BP; bipolar subjects only).

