### **3.5.2.2 Efficacy**

The efficacy of aripiprazole IM depot administration in the gluteal muscle will be assessed by the PANSS (schizophrenia subjects only), CGI-S, Clinical Global Impression - Improvement (CGI-I), Subjective Well-being under Neuroleptic Treatment-Short Form (SWN-S), Montgomery-Asberg Depression Rating Scale (MADRS; bipolar subjects only), Young Mania Rating Scale (YMRS; bipolar subjects only), and Clinical Global Impression - Bipolar Version (CGI-BP; bipolar subjects only).

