**Day 225/Early Termination  $\pm$  2 days (outpatient, all subjects)**

- Document birth control methods.
- Record concomitant medications and review for prohibited or restricted medications.
- Record adjustment of current oral antipsychotic, mood stabilizer, or antidepressant therapy.
- Assess and record AEs.
- Perform a urine pregnancy test (FOCBP only).
- Perform a physical examination.
- Measure weight.
- Take vital signs (systolic and diastolic blood pressure, heart rate, and body temperature).
- Administer a 12-lead safety ECG in triplicate (5 minutes apart).
- Collect hematology, clinical chemistry, and urinalysis clinical laboratory samples.
- Administer the Since Last Visit version of the C-SSRS.
- Assess EPS (SAS, AIMS, and BARS).
- Administer the PANSS (schizophrenia subjects only).
- Administer CGI-S scale and SWN-S (all subjects).
- Administer the MADRS, YMRS, and CGI-BP (bipolar subjects only).
- Draw a PK blood sample between 8 AM and 2 PM.

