## **9 Efficacy Analyses**

Efficacy assessments for all subjects includes Clinical Global Impression - Improvement (CGI-I) and Subjective Well-being under Neuroleptic Treatment - Short Form (SWN-S). The Positive and Negative Syndrome Scale (PANSS) and Clinical Global Impression - Severity (CGI-S) are assessed for schizophrenia subjects only. Montgomery-Asberg Depression Rating Scale (MADRS), Young Mania Rating Scale (YMRS) and Clinical Global Impression - Bipolar Version (CGI-BP) are assessed for bipolar I disorder subjects only. All efficacy assessments will be summarized for the efficacy sample at each mapped trial week by treatment formulation and disease type (if applicable).

PANSS total score (range 30-210) is the sum of the rating scores for 7 positive scale items, 7 negative scale items, and 16 general psychopathology scale items from the PANSS scale. A missing value for any item would result in a missing PANSS total score. PANSS positive subscale score (range 7-49) is the sum of the rating scores for the 7 positive scale items from the PANSS scale. PANSS negative subscale score (range 7-49) is the sum of the rating scores for the 7 negative scale items from the PANSS scale. CGI-S score (range 0-7), CGI-I score (range 0-7), CGI-BP severity score (range 0-7) and

Protocol 031-201-00181

CGI-BP change from preceding phase score (range 0-7) are directly retrieved from CRF data.

SWN-S total score (range 20-120) is the sum of the rating scores for 10 positive scale items (items 2+, 3+, 5+, 7+, 8+, 13+, 15+, 18+, 19+, 20+) and 10 negative scale items (items 1-, 4-, 6-, 9-, 10-, 11-, 12-, 14-, 16-, 17-). SWN-S subscale total score (range 4-24) is the sum of the rating scores for the 4 items in each of the 5 subscales: mental functioning (3+, 7+, 11-, 17-), social integration (8+, 13+, 6-, 14-), emotional regulation (18+, 20+, 4-, 10-), physical functioning (2+, 5+, 9-, 16-), and self-control (15+, 19+, 1-, 12-). For items marked with a '+', the scoring is 'not at all = 1', 'hardly at all = 2', 'a little = 3', 'somewhat = 4', 'much = 5', and 'very much = 6'. For items marked with a '-', the scoring is reversed. response choices and scoring are as follows: not at all = 6, hardly at all = 5, a little = 4, somewhat = 3, much = 2, very much = 1. A missing value of any items in the SWN-S would result in a missing total or a subscale total score.

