The MADRS is utilized as the primary assessment of a subject's level of depressive symptoms and must be administered using a structured interview guide. This scale consists of 10 items each with 7 defined grades of severity on 0 to 6 scale (reported sadness, apparent sadness, inner tension, reduced sleep, reduced appetite, concentration difficulties, lassitude, inability to feel, pessimistic thoughts, and suicidal thoughts). MADRS total score is sum of 10 item score with range from 0~60. The missing score for any 1 item will result in a missing MADRS total score. MADRS total score will be summarized by trial week for each treatment formulation.

The YMRS consists of 11 items assessing the core symptoms of mania and is based on the subject's subjective report of his or her clinical condition. Additional information is based upon clinical observations made during the clinical interview. Each item has 5 defined categories of severity with 4 items graded on a 0 to 8 scale (irritability, speech, content, and disruptive-aggressive behavior) and 7 items graded on a 0 to 4 scale (elevated mood, increased motor activity/energy, sexual interest, sleep, language-thought disorder, appearance, and insight). YMRS total score is sum of 11 item score with range from 0~60. The missing score for any 1 item will result in a missing YMRS total score. YMRS total score will be summarized by trial week for each treatment formulation.

The CGI-BP scale refers to the global impression of the subject with respect to bipolar disorder. The scale rates the subject's severity of illness (CGI-BP-Severity: mania, depression, and overall bipolar illness) and change from baseline visit (CGI-BP Change from Preceding Phase: mania, depression, and overall bipolar illness) based on a 7-point scale (rang 1-7).

Protocol 031-201-00181

LOCF missing data imputation will be performed for all efficacy assessments. Changes from baseline in SWN-S total score and SWN-S subscale total score for all efficacy sample in addition to PANSS total score, PANSS positive subscale total score, PANSS negative subscale total score, CGI-Severity score, MADRS total score, YMRS total score, CGI-BP-Severity score will be summarized using descriptive statistics, if applicable. CGI-Improvement score and CGI-BP change from preceding phase score are also summarized using descriptive statistics, if applicable.

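### The SAP limits CGI-S to schizophrenia, so no post-baseline CGI-S summary is planned for bipolar I subjects, although the protocol makes CGI-S a secondary endpoint for both diagnoses

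*SAP*

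**What the plan says.** **SAP.** Section 6.4, which lists the secondary efficacy variables, gives "Clinical Global Impression Severity (CGI-S; schizophrenia subjects only". Section 9 restates the limit: PANSS and "Clinical Global Impression - Severity (CGI-S) are assessed for schizophrenia subjects only". The same paragraph names the scales that cover both diagnoses, and CGI-S is not among them: "Efficacy assessments for all subjects includes Clinical Global Impression - Improvement (CGI-I) and Subjective Well-being under Neuroleptic Treatment - Short Form (SWN-S". Section 1 says the SAP agrees with the protocol as amended on 31 July 2019 (Amendment 2).

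**Protocol.** Section 3.5.2.2 says that efficacy "will be assessed by the PANSS (schizophrenia subjects only), CGI-S, Clinical Global Impression - Improvement (CGI-I" and the remaining scales. PANSS carries a diagnosis tag and CGI-S does not. Section 3.7.5.2 has CGI-S rated for each subject. The visit lists for both sampling schedules (Tables 3.7.3-2 and 3.7.3-3) are explicit; the Day 225 entry, for example, reads "Administer CGI-S scale and SWN-S (all subjects". Section 7.4.2 plans summaries of the efficacy scales, CGI-S among them and untagged, for the efficacy sample at each visit by treatment group and, where applicable, disease type.

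**The concern.** The two current documents disagree on who contributes to a protocol-defined secondary endpoint. An analyst who follows the SAP would produce post-baseline CGI-S tables for schizophrenia only. Disease type is a randomisation stratum (protocol 3.6.1), so a whole stratum would drop out of the planned summaries of that endpoint without a stated reason.

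The SAP's wording also misdescribes the data. It says whom the scale is assessed in, not only whom it is analysed in, and the protocol has it assessed in everyone. A reader of the eventual report could conclude that the bipolar ratings were never collected.

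CGI-S is also the only clinician-rated severity scale given to both diagnoses. SWN-S is self-reported, CGI-I rates improvement, and the other scales belong to one diagnosis.

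**Working it through.** The plan states no figure on this point that could be reproduced. The check is a comparison of texts, a count of visits, and a range for the number of subjects affected.

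**1. Is the missing tag in the protocol deliberate?** The sentence in 3.5.2.2 tags PANSS as schizophrenia only and MADRS, YMRS and CGI-BP as bipolar only. CGI-S, CGI-I and SWN-S carry no tag. The collection instructions name all subjects for CGI-S. The protocol's intent is therefore clear.

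**2. Is the SAP restriction a single slip?** No. It appears in Section 6.4 and again in Section 9, and CGI-S is also absent from Section 9's list of all-subject scales. The three statements agree with one another and disagree with the protocol.

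**3. Does anything else in the SAP restore bipolar subjects?**
- Section 9 later says that changes in "CGI-Severity score, MADRS total score, YMRS total score, CGI-BP-Severity score will be summarized using descriptive statistics, if applicable". Only the SWN-S scores are named there for the whole efficacy sample, and the closing qualifier leaves the earlier restriction in force.
- Section 9 also says that all efficacy assessments are summarised at each mapped week by treatment and disease type, again only where applicable. Having just said that CGI-S is not assessed in bipolar subjects, the SAP makes it inapplicable to them.
- Section 7.2 includes efficacy assessments among the baseline characteristics shown by disease type. A baseline CGI-S value for bipolar subjects may therefore appear. Post-baseline values are not covered.

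**4. How many visits?** Tables 3.7-1 and 3.7-2 schedule CGI-S at screening and at Days 1, 29, 57, 113, 169, 197 and 225/ET, which is eight time points. Without screening and Day 1, six are post-baseline. In SAP Table 5.2-2 they map to Weeks 4, 8, 16, 24, 28 and 32.

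**5. How many subjects?** Protocol 7.1 gives 152 to 258 enrolled and, at 34% dropout, 100 to 170 completers. Neither document states a bipolar share or quota, so 20% to 50% is an assumption.

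| Basis | Low end | High end |
|---|---|---|
| Enrolled | 0.20 × 152 = 30.4, about 30 | 0.50 × 258 = 129 |
| Completers | 0.20 × 100 = 20 | 0.50 × 170 = 85 |

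The contradiction itself does not depend on the share.

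**The case against.** The strongest reply is that little is lost. Bipolar subjects have their own global severity scale, CGI-BP-Severity, rated at the same visits as CGI-S for mania, depression and overall bipolar illness, and the SAP summarises it. CGI-I and SWN-S stay in the SAP for all subjects. CGI-S is one of seven descriptive secondary efficacy scales in an open-label phase 1b trial whose sample size and interim rules rest on pharmacokinetics alone. All of this stands, and it limits the consequence. It does not remove the contradiction. The protocol has bipolar subjects rated on both CGI-S and CGI-BP at the same visits, so it treats them as separate measures. CGI-I is scheduled only at Day 57 and Day 225/ET and does not measure severity.

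A reader might infer more than the documents support:
- **That a pooled CGI-S comparison across diagnoses is lost.** None is planned. Protocol 7.4.2 describes descriptive summaries and an exploratory mixed model for which it names no scale. SAP Section 9 applies that model to the SWN-S, PANSS and YMRS total scores only, so CGI-S is not modelled even in schizophrenia.
- **That all CGI-S data from bipolar subjects go unreported.** Section 7.2 may show the baseline values, so the secure claim concerns post-baseline visits.
- **That the narrowing is concealed.** It is stated openly, twice. What is missing is a reason. Parts of the SAP are redacted, so a rationale there cannot be ruled out, but its table of contents lists no section on changes from the protocol.

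**Conclusion.** The inconsistency is real, and the SAP is wrong as written on this point. It omits the post-baseline CGI-S summaries for bipolar I subjects that protocol 7.4.2 calls for, while stating agreement with that protocol.

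The consequence is modest. It is limited to descriptive tables for one secondary endpoint in one stratum, with no hypothesis test or trial decision attached. The 129 at the top of the enrolled range would be reached only with full enrolment and an even split between diagnoses, and even then not all of those subjects would contribute at every visit. At Day 225, the completer range of about 20 to 85 is the better guide. Both ranges rest on the assumed bipolar share of 20% to 50% and on the protocol's own enrolment and dropout figures.

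**What to change.** Delete the schizophrenia-only limit on CGI-S in SAP 6.4 and Section 9, and move CGI-S to Section 9's list of scales for all subjects. State that CGI-S values and changes from baseline are summarised for the efficacy sample by trial week, treatment and disease type, on both the observed-case and last-observation-carried-forward datasets, as protocol 7.4.2 provides.

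If the sponsor does intend to rely on CGI-BP-Severity alone in bipolar subjects, the SAP should say so as a declared departure from protocol 3.5.2.2 and 7.4.2, give the reason, and correct the statement about whom CGI-S is assessed in.

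The cost of the main fix is a wording change and a few more summary tables. No new data, visits or subjects are needed.

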## **7 Summary of Trial Data**

### **7.1 Subject Disposition**

Disposition of subjects including screened subjects and/or randomized subjects will be reported by treatment formulation, PK sampling schedule (i.e., robust or sparse) and disease type (i.e., schizophrenia or bipolar I disorder) in addition to summary by center. Durations of subjects staying in the treatment phase will be summarized by week, treatment formulation, PK sampling schedule and disease type. Reasons for discontinuations will be tabulated by treatment formulation, PK sampling schedule and disease type. Subjects who are evaluated at the last scheduled visit (i.e., Day 225 visit for aripiprazole 2M LAI 960 mg and aripiprazole IM depot 400 mg) during the treatment phase will be defined as trial completers.

### **7.2 Demographic and Baseline Characteristics**

Demographic characteristics (including age, weight, height, BMI, sex, race, and ethnicity) will be summarized for randomized sample using descriptive statistics (frequency, mean, median, standard deviation, maximum, minimum, and percentage when applicable) and reported by treatment formulation, PK sampling schedule and disease type.

Disease characteristics at baseline and psychiatric history (including efficacy assessments age of initial diagnosis for schizophrenia or bipolar I disorder) will be presented for the randomized sample by treatment formulation, PK sampling schedule and disease type. In calculating age of first diagnosis for schizophrenia or bipolar disorder, if both month and day are missing, June 1 is used. If only day is missing, date of 1 is used. If only month is missing, month June is used.

### **7.3 Treatment Compliance**

Compliance of trial medication for aripiprazole 2M LAI 960 mg and IM depot 400 mg will be summarized for the randomized sample. Compliance is defined as receiving the aripiprazole IM depot 400 mg injection in the minimum interval of 26 days or 960 mg aripiprazole 2M LAI injection at least 54 days after the prior injection.

Protocol 031-201-00181

Compliance of trial medication of oral aripiprazole in first 2 weeks is derived from total days taking oral tablets divided by 14 days for aripiprazole IM depot 400 mg injection group or 7 days for 960 mg aripiprazole 2M LAI injection group or total days in the trial if patients withdraw from the study before day 15. Proportion of subjects reaching at least 50%, 60%, 70%, 80% and 90% compliance to oral tablets are tabulated by treatment group, disease type for subjects with PK robust sampling schedule.

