### 3.2.3 Oral Overlap

At the time of administration of the first dose of IMP, subjects will begin a 7- to 14-day period (oral overlap) where they will transition from their current oral antipsychotic to include injections of IMP, according to the scenarios described in [Table 3.2.3-1](#).

Subjects currently stabilized on a non-aripiprazole oral antipsychotic who are enrolled to a sparse sampling schedule will continue on their medication and subjects who are enrolled to a robust sampling schedule will switch to 10 to 20 mg oral aripiprazole (dose determined by the investigator). Subjects will take their oral antipsychotic medications concurrently with IMP for 7 days after the first administration of aripiprazole 2M LAI 960 mg or 14 days after the first administration of aripiprazole IM depot 400 mg. The oral antipsychotic will be discontinued after 7 days of administration of aripiprazole 2M LAI 960 mg and after 14 days of administration of aripiprazole IM depot 400 mg.

For subjects currently stabilized on oral aripiprazole, the recommended supplemental oral aripiprazole dose will be reduced to 10 mg/day with the first dose of IMP for subjects with a previous dose of 10 to 20 mg/day or to 15 mg/day for subjects with a previous dose of > 20 to 30 mg/day ([Table 3.2.3-2](#)).

There will be no oral overlap for subjects who are taking Abilify Maintena® as their current antipsychotic medication. Subjects who are on Abilify Maintena as their current antipsychotic cannot be enrolled until their next scheduled dose is required as specified in the label, and they cannot receive IMP any earlier than 26 days after the last Abilify Maintena injection. In this scenario, the investigator should carefully consider the screening period and the timing of randomization in relation to the first dose of IMP and previous dose of Abilify Maintena.

Given the addition of a second antipsychotic, investigators should consider reducing the dose of the current oral antipsychotic, mood stabilizer, or antidepressant medications to the mid to lower range of the recommended dose range described in the labeling.

Aripiprazole tablets for oral overlap will be provided from a commercial supply.

Protocol 031-201-00181

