**Day 8 (inpatient, all subjects)**

- Subjects assigned to aripiprazole 2M LAI 960 mg will **discontinue** taking 10 to 20 mg oral aripiprazole and/or current oral antipsychotic (as applicable) until the end of the trial. Subjects may resume treatment on their previous oral non-aripiprazole antipsychotic after Day 28, if there is evidence of clinical deterioration based on the judgment of the investigator.
- Record concomitant medications and review for prohibited or restricted medications.
- Record adjustment of current oral antipsychotic, mood stabilizer, or antidepressant therapy.
- Assess and record AEs.
- Take vital signs (systolic and diastolic blood pressure, heart rate, and body temperature).
- Assess EPS (SAS, AIMS, and BARS).
- Draw a PK blood sample between 8 AM and 2 PM.

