## 3 Trial Design

This is a phase 1b, open-label, multiple-dose, randomized, parallel-arm, multicenter (approximately 20 trial sites) trial in adult subjects with schizophrenia or bipolar I disorder. The trial design schematic is shown in [Figure 3-1](#).

Subjects between the ages of 18 to 64 years old, inclusively, are randomized (1:1 randomization) to receive multiple doses of 2 month (2M) long-acting injectable (LAI) 960 mg (4 injections) or aripiprazole IM depot 400 mg (8 injections) over the course of 32 weeks. Aripiprazole 2M LAI 960 mg are administered at 56-day intervals and aripiprazole IM depot 400 mg are administered at 28-day intervals (+/- 2 days). A final visit occurs 56 (+/- 2) days after the last dose of aripiprazole 2M LAI 960 mg or 28 (+/- 2) days after the last dose of aripiprazole IM depot 400 mg. The randomization is

Protocol 031-201-00181

stratified by PK sampling schedules (robust sampling schedule or sparse sampling schedule) and disease type (schizophrenia or bipolar I disorder). If enrollment of the number of subjects required for the robust sampling schedule is completed, the robust sampling trial sites may enroll new subjects to the sparse sampling schedule.

The trial consists of a screening period of up to 30 days, a treatment period of 169 ( $\pm 2$ ) days, and a follow-up period of 56 ( $\pm 2$ ) days after administration of the final dose for the aripiprazole 2M LAI 960 mg treatment group, or a treatment period of 197 ( $\pm 2$ ) days, a follow-up period with 28 ( $\pm 2$ ) days after administration of the final dose for the aripiprazole IM depot 400 mg treatment group. Individual participation is approximately 255 ( $\pm 2$ ) days.

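### SAP 7.3 counts late injections of any length as compliant, and its oral-tablet denominator under-scores fully adherent 2M LAI subjects who leave on Days 8 to 14

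*SAP*

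**What the plan says.** **Injections.** SAP 7.3 summarises compliance in the randomized sample. An injection is compliant if given "in the minimum interval of 26 days or 960 mg aripiprazole 2M LAI injection at least 54 days after the prior injection". No maximum is stated. SAP section 3 describes the schedule as "Aripiprazole 2M LAI 960 mg are administered at 56-day intervals and aripiprazole IM depot 400 mg are administered at 28-day intervals (+/- 2 days". That sentence could be read as attaching the window to the monthly product only, but protocol 3.1 and 3.2.1 attach ± 2 days to each interval. Protocol 3.7 adds a second tolerance: visits may fall up to 2 days either side of the target visit date, for sparse-schedule subjects and for robust-schedule subjects after discharge.

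**Oral tablets.** SAP 7.3 divides each subject's tablet days by the planned overlap, which is 14 days in the 400 mg arm and 7 in the 2M LAI arm. For early leavers the divisor becomes "total days in the trial if patients withdraw from the study before day 15". The early-withdrawal clause does not distinguish the arms. The proportions reaching 50, 60, 70, 80 and 90% are tabulated by treatment group and disease type, for the robust schedule only. The planned overlap differs by arm: "The oral antipsychotic will be discontinued after 7 days of administration of aripiprazole 2M LAI 960 mg and after 14 days" for the 400 mg product (protocol 3.2.3). The Day 8 entry of the robust schedule (Table 3.7.3-3) has 2M LAI subjects stop taking "10 to 20 mg oral aripiprazole and/or current oral antipsychotic (as applicable) until the end of the trial".

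**Elsewhere.** SAP 7.5 summarises dosing deviations by type, with a subject listing. SAP 8.1 summarises the trial day of each injection.

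**The concern.** A compliance table should show how far dosing followed the schedule. The schedule is two-sided and the SAP's rule is one-sided, so the table can register an early injection but never a late one. In a trial that compares two injection intervals, lateness is a departure that a reader would expect this table to show.

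The oral rule has a different fault. A Day 15 cut-off suits a 14-day overlap. Applied to a 7-day overlap, it adds days to the denominator on which the subject was meant to be off tablets. The error falls on one arm only, in a table laid out to compare arms.

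At stake is the accuracy of two descriptive summaries.

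**Working it through.** **1. The SAP's own limits.** From the planned intervals and the ± 2-day tolerance, the lower edges are 28 − 2 = 26 and 56 − 2 = 54 days. These match SAP 7.3 exactly. The upper edges are 28 + 2 = 30 and 56 + 2 = 58 days, and SAP 7.3 does not contain them.

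**2. What the one-sided rule passes.**

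| Arm | Gap (days) | SAP 7.3 | Within the planned interval ± 2 |
|---|---|---|---|
| 400 mg | 26, 28, 30 | compliant | yes |
| 400 mg | 31, 35, 56 | compliant | no |
| 2M LAI | 54, 56, 58 | compliant | yes |
| 2M LAI | 59, 70, 112 | compliant | no |

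A 56-day gap in the 400 mg arm equals a skipped monthly dose.

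**3. The two tolerances differ.** Under the visit-date tolerance in protocol 3.7, the Day 57 and Day 85 doses could fall on Days 55 and 87, a gap of 87 − 55 = 32 days, or on Days 59 and 83, a gap of 83 − 59 = 24 days. For 2M LAI, the Day 57 and Day 113 doses could be 115 − 55 = 60 or 111 − 59 = 52 days apart. Visits that all meet the visit-date tolerance can therefore fall outside 26–30 or 54–58 days, and some fall below even the existing minimum.

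**4. Oral compliance with every planned tablet day taken.** SAP 5.2 counts the first injection as Day 1, so leaving on Day d gives d days in the trial. The score is min(d, planned overlap) / d if d < 15, and planned overlap / planned overlap = 100% otherwise.

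| Withdrawal day | 2M LAI (7 days planned) | 400 mg (14 days planned) |
|---|---|---|
| 1–7 | 100% | 100% |
| 8 | 7/8 = 87.5% | 8/8 = 100% |
| 9 | 7/9 = 77.8% | 100% |
| 10 | 7/10 = 70.0% | 100% |
| 11 | 7/11 = 63.6% | 100% |
| 12 | 7/12 = 58.3% | 100% |
| 13 | 7/13 = 53.8% | 100% |
| 14 | 7/14 = 50.0% | 14/14 = 100% |
| 15 onward | 7/7 = 100% | 14/14 = 100% |

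The fully adherent 2M LAI subject misses the 90% category on every day from 8 to 14, the 80% category from Day 9, the 70% category from Day 11 and the 60% category from Day 12.

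Counting elapsed days (d − 1) instead gives 7/7 = 100% on Day 8 and 7/13 = 53.8% on Day 14. But it also gives 7/6 = 116.7% on Day 7, so it is not a workable reading.

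**5. How many subjects.** SAP section 3 plans up to 38 robust-schedule subjects per group, with at least 25 completing. At most 38 − 25 = 13 per group are thus expected to leave over the whole trial. The documents give no breakdown by week. With all 38 in the denominator, each mis-scored subject lowers the 2M LAI 90% category by 1/38 = 2.6 percentage points.

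**6. With the oral denominator corrected.** Dividing by min(d, planned overlap) gives 100% on every withdrawal day in both arms.

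**The case against.** The best defence is that late injections are reported elsewhere. The dosing-deviation summary and listing (SAP 7.5) and the trial day of each injection (SAP 8.1) both show them, and protocol 3.12 requires the actual time and dose to be recorded. This stands. A reader might infer that SAP 7.3 is the only planned adherence summary, so that lateness would go unseen. The documents do not support that. The defence does not repair the compliance table, which still labels such injections compliant.

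A reader might also infer that late dosing lowers the primary troughs by a known amount. With the 24.0-day half-life in protocol 1.3, 2^(−7/24) = 0.817 and 2^(−14/24) = 0.667, or about 18% and 33% lower at 7 and 14 days late. Those figures describe the concentration just before a late injection. The primary values are C56 and C28 after the final injection, and even the direction is not fixed. If the fourth 2M LAI dose is given on Day 176 instead of Day 169, a Day 225 sample is 49 days postdose, with less time for decline. A sample 56 days postdose falls on Day 232, outside the Day 223–227 window of SAP Table 5.2-1. Nor does the compliance definition enter any analysis set (SAP 5) or the primary model (SAP 10.1). The inference fails.

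Two further objections stand in part. A 26–30 and 54–58 day rule cannot simply be inserted, because protocol 3.7 permits wider gaps; the two tolerances must be reconciled first. And the oral error is small: it needs a robust-schedule 2M LAI subject to leave in one particular week, when such subjects are generally housed in the unit, and 50% is the Day 14 extreme. A programmer might silently use 7 days there, but the text does not say so.

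**Conclusion.** Wrong as written, with limited consequences.

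- **Injections:** the rule reproduces only the lower half of the planned ± 2-day tolerance, so gaps of 31 days or more (400 mg) and 59 days or more (2M LAI) count as compliant without limit. The size of the overstatement cannot be given, because it depends on how many injections are late.
- **Oral tablets:** fully adherent robust-schedule 2M LAI subjects who leave on Days 8 to 14 score 87.5% down to 50%, while their 400 mg counterparts score 100%. This rests on the literal text and on the SAP's Day 1 convention.

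Both effects stay within descriptive compliance tables, and the oral one probably touches few subjects. No primary PK result depends on either definition.

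**What to change.** In SAP 7.3:

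1. Make injection compliance two-sided for reporting, using the documents' own ± 2-day tolerance. First reconcile the interval tolerance (26–30 and 54–58 days) with the target-visit tolerance in protocol 3.7, and state which one the table uses. This concerns how adherence is reported; it proposes no change to dosing.
2. Set the oral denominator to the smaller of the planned overlap days (7 for 2M LAI, 14 for 400 mg) and days in the trial.

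The cost is a few lines of SAP wording and a small change to the compliance derivation. No new data are needed. Reported injection compliance may be slightly lower, and 2M LAI oral compliance may be slightly higher.
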